## **6.7 BASELINE, TIME WINDOWS AND CALCULATED VISITS**

No visit windows will be used. The CRF nominal visits will be applied for the analysis. Unscheduled visits are not expected and if any they will not be counted for primary and secondary endpoints. However, they will be considered for the safety analysis regarding Adverse Events (if any).

The baseline value will be the first measurement made after the enrolment to the study.

Baseline information will be presented appropriately in the “by visit” summaries.

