### **9.3.2 Withdrawal Criteria**

The patients reserve the right to withdraw consent at any time during the study, without the need for justification and without any impact on their future treatment and care.

Withdrawal of consent means that the patient does not wish or cannot continue to participate in the study any more.

The reasons for withdrawal may include the following:

- Patient or legally accepted representative withdraws informed consent for participation in the study.
- Inclusion or possible participation in any clinical trial, any time within the follow up period of the study, in which the patient has been exposed or is going to be exposed to an investigational product (pharmaceutical product or medical device) or intervention.
- The patient was erroneously included in the registry
- Decision of the investigator/physician
- Important deviation/divergence from the protocol.

The Clinical Monitor at BI or BI's designees must be immediately notified if a patient is discontinued prematurely for any of the instances reasons cited above.

Patients that withdraw from the study should be asked about the reason(s) for withdrawal and the occurrence of adverse events, and should be examined and evaluated by the investigator according to the procedures that are defined in the Final Visit (unless reason for discontinuation is erroneous enrolment of the patient into the study at baseline and unless patient has actively withdrawn consent for any kind of future contacts).

If the patient specifically withdraws consent for future contact about the collection of further information, there will be no such contact whatsoever. However, it is possible to collect information regarding their survival status, if they are publicly available.

The investigators also reserve the right to remove a patient from the study, if according to their clinical judgment this is the necessary for the patient's welfare.

If a patient is removed or withdrawn from the study for any reason, the date, vital status and reason must be documented in the relevant section of the electronic Case Report Form (eCRF).

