### **9.3.3      Study Visits**

The registry is scheduled to run for 4 years in total (2 years recruitment + 2 years follow up) (April 2017 to April 2021).

During the follow up period, data will be collected on standard clinical visits which usually are scheduled around: 3-months (+/- 1 month), 6-months (+/- 1 month), 12-months (+/- 2 month), 18-months (+/- 2 month) and 24 months (+/- 2 months), until the end of participation in the study. In case of events, unscheduled visits may be required.

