#### **9.4.5 Covariates**

Due to the non - interventional nature and design of the observational study, this registry does not require diagnostic/therapeutic procedures or strict timeline visit schedule. Patients will receive treatment according to standard clinical practice with regards to visit frequencies, type of performed assessments and according to local prescription requirements.

Following identification of a potential patient, the investigator will follow the below listed procedures:

1. Review of individual patient's medical history, to confirm that the inclusion/exclusion criteria are met.
2. Explanation of the study objectives to the patient and receipt of signed and dated informed consent, after providing the patient with sufficient time to read carefully and understand the information sheet.
3. Data collection from the medical records of eligible for enrollment patients, as required by eCRF, and eCRF completion.

Please refer to [Section 11.2](#) for details regarding Adverse Event and Serious Adverse Event Collection and Reporting.

A tabulated schedule of assessments that provide information regarding the recommended timeline of data collection and represents the standard clinical care of IPF treated patients is listed below in [Table 1](#). The exact definitions of the variables can be found in Appendixes 2-5.

Table 1. List of variables to be documented (if available) at scheduled visits

Variable (Please refer to Annex 4 )	Assessment	Follow up**
Eligibility criteria	x	
Baseline information (assessment)		
(Socio-)demographic variables: age, gender, race, height, index employment status, insurance status	x	
Weight, blood pressure, heart rate	x	x
(Possible) IPF risk factors		
Cigarette smoking incl. pack years (Categorized as never/past/current/unknown. For past/current, specify packs/year and for past, number of years smoking one pack per day); environmental and occupational exposure; alcohol and substance abuse; exposure to drugs associated with IPF ; exposure to viral infection possibly related to IPF; gastro-oesophageal reflux; genetic factors (family history); others	x	
Co-morbidities (Please refer to Annex 5 )	x	x
IPF		
Baseline information (assessment) on IPF		
First symptoms; date of first diagnosis, dates and results of HRCT, surgical lung biopsy, bronchoalveolar lavage.	x	
Symptoms		

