## **9.5 DATA SOURCES**

The study will mainly include the recording of new data through a web based system for data collection. Data will be collected by the study doctors as they occur according to standard clinical practice in the approximate visiting schedule indicated above.

Source (primary) patient data related to their medical and IPF history will be collected by the investigators from the patient's medical files/records and will be documented in the relevant eCRF section.

Data regarding treatment modifications, concomitant treatments, study related routine clinical assessments, adverse events (ADRs) and survival status will also be collected. If a patient withdraws early from the study, they will be contacted via telephone at the end of the Study in order to evaluate their survival status. Another follow-up assessment should be performed if possible (unless reason for discontinuation is erroneous enrolment of the patient into the study at baseline), and data should be entered on the eCRF of the next planned visit unless the patient has actively withdrawn consent for any kind of future contacts.

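### Early-withdrawal assessments go on the next planned visit's eCRF page and the SAP analyses by page label, so values taken up to about 6 to 8 months early can be reported as month 12, 18 or 24 results

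*SAP*

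**What the plan says.** - **Where the data go.** For a patient who leaves early, Protocol 9.5 asks for a further assessment if possible and says that "data should be entered on the eCRF of the next planned visit", unless the patient has refused all further contact.
- **What the assessment is.** Protocol 9.3.2 has withdrawing patients "evaluated by the investigator according to the procedures that are defined in the Final Visit". Neither section gives a time for it, although 9.3.2 reads as an examination on leaving.
- **How visits are defined for analysis.** SAP 6.7: "No visit windows will be used. The CRF nominal visits will be applied for the analysis". It continues: "Unscheduled visits are not expected and if any they will not be counted for primary and secondary endpoints".
- **What the protocol planned.** Protocol 9.3.3 places follow-up visits at "3-months (+/- 1 month), 6-months (+/- 1 month), 12-months (+/- 2 month), 18-months (+/- 2 month) and 24 months (+/- 2 months"). Protocol 9.4.5 adds that "this registry does not require diagnostic/therapeutic procedures or strict timeline visit schedule".
- **What is reported by visit.** SAP 5.1 lists change from baseline at 3, 6, 12, 18 and 24 months for vital signs and for 6-minute walk distance and VO2max. SAP 7.8.2 and 7.8.3 do the same by visit for laboratory values and vital signs. Lung function is to be described, with no change from baseline listed.
- **Missing data.** SAP 6.6 rules out imputation and last observation carried forward.

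**The concern.** Taken together, the two rules let a measurement made soon after one visit be reported as the result of the next, with nothing in the output to show it. The SAP has no rule based on the measurement date, no early-termination visit and no flag. Its exclusion of unscheduled visits does not help, because the value sits on a planned-visit page. The same measurement would be left out if labelled unscheduled and is counted if entered as Protocol 9.5 instructs. The result partly resembles the carrying forward that SAP 6.6 rejects.

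Progression is part of the main objective, and Protocol 7.1 describes IPF as progressively worsening. A value taken too early and labelled late would then tend to show less decline than the patient would have had at the labelled time. What is at stake is the accuracy of the by-visit functional summaries, above all at the later visits, where the gap between visits is 6 months.

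**Working it through.** The plan gives no figure to reproduce here: no dropout rate and no rate of decline. Only the timing comes from the documents; the rest is illustration under stated assumptions.

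**1. How early can a value be?** Earliness is the labelled month minus the time of the previous visit, from Protocol 9.3.3.

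| Page | Previous visit (nominal; early edge) | Maximum earliness |
|---|---|---|
| Month 12 | 6; 5 | 12 − 6 = 6; 12 − 5 = 7 months |
| Month 18 | 12; 10 | 18 − 12 = 6; 18 − 10 = 8 months |
| Month 24 | 18; 16 | 24 − 18 = 6; 24 − 16 = 8 months |

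The protocol tolerance at these visits is 2 months. If withdrawal is uniform over the 6-month interval, mean earliness is 3 months, and (6 − 2)/6 = 67% of such values fall before the window of the visit they are labelled with.

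**2. What one value shows.** Under linear decline, a value taken at month *t* shows *t/T* of the change at labelled month *T*. At mid-interval this is 9/12 = 75%, 15/18 = 83% and 21/24 = 88%. Just after the previous nominal visit it is 6/12 = 50%, 12/18 = 67% and 18/24 = 75%.

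**3. Effect on the visit mean.** Let *f* be the share of a page's values that are withdrawal values, *r* the withdrawers' rate of decline relative to completers, and *m* the mid-interval month. Both *f* and *r* are assumptions.

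Relative understatement = *f r* (1 − *m/T*) / [(1 − *f*) + *f r*]

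| Page | f = 5%, r = 1 | f = 10%, r = 1 | f = 20%, r = 1 | f = 20%, r = 2 |
|---|---|---|---|---|
| Month 12 | 1.3% | 2.5% | 5.0% | 8.3% |
| Month 18 | 0.8% | 1.7% | 3.3% | 5.6% |
| Month 24 | 0.6% | 1.3% | 2.5% | 4.2% |

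Example, month 12, *f* = 20%, *r* = 2: 0.20 × 2 × 0.25 / (0.80 + 0.40) = 0.10/1.20 = 8.3%.

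**4. Would it be better just to drop these values?** With completers' change set to 1, dropping them gives a mean of 1, and keeping them under the nominal label gives (1 − *f*) + *f r m/T*. Dropping understates decline more than keeping when *r m/T* > 1, that is, when *r* exceeds *T/m*: 12/9 = 1.33 at month 12, 18/15 = 1.20 at month 18 and 24/21 = 1.14 at month 24. Simple deletion is therefore not a safe remedy.

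**The case against.** The best defence is that this is a descriptive registry without hypothesis tests or a strict schedule, that nominal visits are a defensible choice in that setting, and that the effect is small. Much of it stands.

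- **Timing is not stated.** Protocol 9.5 does not say when the extra assessment takes place. If it were done when the next visit fell due, the label would be right. The problem depends on reading 9.5 with 9.3.2.
- **Few values may be affected.** The assessment is made only if possible, death and transplantation end follow-up, and tests are done only in routine practice. Some withdrawal assessments may hold no new functional test.
- **Not every endpoint is reached.** A reader might infer that change in FVC and DLCO is distorted. The SAP lists change from baseline only for vital signs, 6-minute walk/VO2max and laboratory values, so lung function is touched only if it is summarised by visit. A model of steady decline has no basis for blood pressure or transaminases.
- **Routine visits.** A reader might also infer that every early or late routine visit adds to the same bias. Early visits understate decline and late ones overstate it, and the protocol windows are symmetric, so no net direction follows.
- **Direction.** Protocol 7.4 says that some patients remain stable and others progress rapidly. Understatement is a tendency, measured against the patient's own later, unobserved value.

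What does not stand is the view that the plan already handles these values. No rule in either document identifies or re-dates them.

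**Conclusion.** The gap is real and modest in size. If the assessment is done at withdrawal, Protocol 9.5 and SAP 6.7 together allow a value about 6 months early, at the extreme 7 (month 12) or 8 (months 18 and 24), to be reported as that visit's result, against the protocol's own tolerance of 2 months. For functional measures in a progressive disease this would tend to understate decline: by roughly 1.3 to 5% of the mean change at month 12 with equal rates of decline, 8.3% in the least favourable case shown, and less at months 18 and 24. These percentages rest on linear decline, withdrawal on average at mid-interval and assumed shares of 5 to 20%; the documents supply none of these. They do not support a firm claim that decline is understated, or that lung-function, laboratory and vital-sign results are all biased. The case for a change is that it is cheap and lets the reader see which values are early.

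**What to change.** Replace the visit rule in SAP 6.7 along these lines:

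1. Assign each measurement to an analysis visit by its own date, using the Protocol 9.3.3 windows (months 2–4, 5–7, 10–14, 16–20 and 22–26 from baseline). If several values fall in one window, use the one nearest the target month.
2. Where no test date is recorded, use the visit date. Annex 4 lists dates for pulmonary function, vital signs and laboratory values, but has no entry for 6-minute walk or CPET.
3. Report values outside all windows in a separate *out-of-window / early withdrawal* row, with actual months since baseline. Identify withdrawal assessments from the withdrawal date that Protocol 9.3.2 already requires, so that a continuing patient's late or early routine visit is not described as a withdrawal.
4. Add a sensitivity summary that keeps the nominal-visit assignment, because taking withdrawers' values out of the visit rows can itself understate decline if they decline faster (the factors of 1.33, 1.20 and 1.14 above).

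The cost is SAP wording and some programming, with fewer values in some visit rows. No eCRF or protocol change is essential, but the timing of the withdrawal assessment in Protocol 9.3.2 and 9.5 should be reconciled.

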- Clinical events and hospitalizations especially due to: (acute) respiratory worsening, including pneumonia, exacerbations of IPF, occurrence of pulmonary or cardiovascular complications, pulmonary rehabilitation, pulmonary embolism, pneumothorax, or cardiac failure
- Management of IPF and physician contacts

During follow up visits (prospectively until up to 2 years at least from the inclusion) 3-months (+/- 1 month), 6-months (+/- 1 month), 12-months (+/- 2 month), 18-months (+/- 2 month) and 24 months (+/- 2 months), documentation of events (or last follow up visit) will be carried out. The collection of data will be performed during standard clinical practice visits (i.e. visits should not be performed via telephone contact). In a special event where the physical presence of the patient is not possible, e.g. in case of temporary inability of the patient to visit the expert center, this visit could be performed through telephone contact and this should be recorded in patient's history. Every effort should be made, however, to ensure that the next visit will be performed as planned by the patient in person. If this is not possible the patient will be censored for the rest of the study. Patient will be followed up until death, lung transplantation, consent withdrawal or end of study, whichever comes first and will be censored if one of the events occurs. The following data will be documented:

- Clinical course of IPF (e.g. regarding symptoms, lung functionality, exercise ability, if available)
- Vital status
- Physical and vital signs examination
- Cardiopulmonary exercise testing (6-minute walk distance and CPET, if performed)
- Autoimmune Biomarker results (No additional specimen will be collected. Only already existing data will be used from exams that have been performed according to the routine clinical practice of the physicians)
- Risk of bleeding and thrombosis
- Outcomes of interest (such as acute respiratory worsening, exacerbations, hospitalization due to any cause and due to IPF). Please, refer to [Annex 3](#)
- Recording of therapeutic algorithms (change/complement/interrupt treatment) and non-pharmacological treatment (e.g. start of LTOT, new listing for lung transplantation)
- Physician's clinical rating of the probable course of IPF (stable, slow or rapid

progression)

- Assessment of treatment intensity, frequencies and resource use for pharmacoeconomic analyses for the treatments described under 11.3

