9.4.5.1 Dyspnea, cough fatigue, dizziness, chest pain, anxiety [20]	x	x
Functional assessment		
Lung function test (VCin, FVC, FEV1, TLC; DLCO; pO2, pCO2) [21]		
6-minute walk distance	x	x
Cardiopulmonary exercise testing (CPET;)		
Serologic evaluation– Autoimmune Biomarkers (laboratory values)		
Rheumatoid factor, anti-cyclic citrullinated peptide, and anti-nuclear antibody titer and pattern*	x	
Others e.g. SCL-70, SS-A, SS-B		x

Proprietary confidential information © 2018 Boehringer Ingelheim International GmbH or one or more of its affiliated companies

BNP/NT-pro BNP		
Hb, AST, ALT, total bilirubin		
Pharmacological treatment( start date, stop date and daily dose)		
Past/discontinued: drugs (e.g. steroids yes/no/unknown). Detailed list of drugs in Annex 4	x	x
Current: drugs by class and/or name	x	x
Participation in IPF trial	x	x
Non-pharmacological treatment	x	x
Long-Term-Oxygen-Therapy (liquid and/or concentrate)	x	x
Lung transplantation score and assessment if the patient is currently listed for participation in lung transplantation	x	x
Physician assessment		
Physician's clinical rating of the probable course of IPF (stable, slow or rapid progression), based on available FVC results, DLCO results, physical examination, hospitalizations/events between the visits	*** x	x
Management of IPF and physician contacts		
Number of physician visits (own office, other physicians)	*** x	x
Number and type of IPF related procedures	*** x	x
Outcomes of Interest (please refer to Annex 3)		
	*** x (except for mortality, hospitalization, please see below)	x
Clinical events and hospitalizations		
specifically due to: (acute) worsening of respiratory function including pneumonia; IPF-exacerbations; manifest pulmonary or cardiovascular complications; pulmonary rehabilitation; pulmonary embolism; pneumothorax; cardiac failure (please refer to Annex 3 for detailed description of the outcomes of interest).	*** x	x
Number of days in hospital or in rehabilitation; work days lost due to IPF	*** x	x
Physical examination and vital signs		
Risk of bleeding and thrombosis	x	x

Survival status (vital status)(please refer to Annex 3)		x
--	--	---

For abbreviations, please refer to glossary.

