### **9.8.1 Main Analysis**

The objective of this registry is neither to confirm nor to reject any predefined hypothesis; therefore the nature of the statistical analyses will be exploratory and descriptive.

Continuous variables will be listed as median with interquartile and other percentages, and as mean value with standard deviation (SD), along with minimum and maximum values (depending on the underlying distribution). Categorical values will be listed as absolute and relative frequencies. All events during follow up will be described as incidence rates with 95% confidence interval (CI).

Stratified analyses will be performed among newly diagnosed patients (< 6 months) as well as patients that were diagnosed in the past ( $\geq 6$  months). In case of conflicting results those of the newly diagnosed will be the decisive. Due to limited number of patients and population heterogeneity, no comparison between treatments can be done and no causal relationship conclusion can be derived (no hypothesis testing). Statistical analyses will be performed with IBM SPSS Statistics (Version 19.0).

If it was not avoidable to select patients from sites with other ongoing registries, patients enrolled in other registries in parallel need to be analyzed separately. In case of difference the results for the BI registry patients are decisive.

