### Collection of AEs

The study design is of non-interventional nature and the study is conducted within the conditions of the approved marketing authorisation. Sufficient data from controlled interventional trials are available to support the evidence on the safety and efficacy of Nintedanib. For this reason the following AE collection and reporting requirements have been defined.

The following must be collected by the investigator in the (e)CRF from signing the informed consent onwards until the end of the study:

- all ADRs related to Nintedanib, taken for idiopathic pulmonary fibrosis (serious and non-serious),
- all AEs with fatal outcome in patients exposed to Nintedanib, taken for idiopathic pulmonary fibrosis

All ADRs, including those persisting after study completion must be followed up until they are resolved, have been sufficiently characterized, or no further information can be obtained.

The investigator carefully assesses whether an AE constitutes an ADR using the information below.

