- Description of Clinical events and hospitalizations especially due to: (acute) respiratory worsening, including pneumonia, exacerbations of IPF, occurrence of pulmonary or cardiovascular complications, pulmonary rehabilitation, pulmonary embolism, pneumothorax, or cardiac failure.

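### SAP 6.7 excludes unscheduled visits from the primary and secondary endpoints, although the protocol foresees such visits when events occur and wants all events described

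*SAP*

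**What the plan says.** SAP 6.7 applies the nominal CRF visits and no visit windows. It then says: "Unscheduled visits are not expected and if any they will not be counted for primary and secondary endpoints". Its one exception keeps unscheduled visits for the safety analysis of adverse events.

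The protocol differs. Section 9.3.3, after listing visits at 3, 6, 12, 18 and 24 months, adds: "In case of events, unscheduled visits may be required". Section 9.8.1 says: "All events during follow up will be described as incidence rates with 95% confidence interval (CI").

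SAP 5.1 places the affected outcomes among the primary endpoints: "Description of Clinical events and hospitalizations especially due to: (acute) respiratory worsening, including pneumonia, exacerbations of IPF". It also lists acute worsening, exacerbations and hospitalisation in newly diagnosed patients. SAP section 4, on changes to the planned analysis, does not mention the exclusion.

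**The concern.** The protocol expects an off-schedule visit because something has happened to the patient. The SAP says such visits will not happen and, if they do, sets them aside for the very endpoints that describe what happened. A programmer following SAP 6.7 would contradict Protocol 9.8.1, and one following 9.8.1 would contradict SAP 6.7. Two analysts could therefore report different event frequencies from one database.

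Any loss would not be random. A patient who attends the next nominal visit can have the event recorded there. A patient who dies, is transplanted or cannot be reached has no such visit. The events at risk therefore belong mainly to the sickest patients, and losing them can only lower the reported frequency.

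**Working it through.** The plan gives no figure for this point, so there is nothing to reproduce. The check compares the texts and then sets a scale.

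**Which events are exposed**

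- *Recovered at a later nominal visit.* Protocol Table 1 bases the physician's rating at each visit partly on "hospitalizations/events between the visits". Protocol section 8 collects treatment changes since the previous visit. Annex 3 gives hospitalisations entry and discharge dates.
- *Recovered after early withdrawal.* Protocol 9.3.2 asks for a final-visit evaluation. Protocol 9.5 asks for a further assessment if possible and says "data should be entered on the eCRF of the next planned visit".
- *No stated route.* Protocol 9.4 ends observation as follows: "Patient will be followed up until death, lung transplantation, consent withdrawal or end of study, whichever comes first". For a non-fatal event between the last nominal visit and death or transplantation, or in a patient who cannot be reached, no later visit form is described.
- *The adverse-event exception.* Protocol 11.2 limits adverse-event collection to nintedanib adverse reactions and "all AEs with fatal outcome in patients exposed to Nintedanib, taken for idiopathic pulmonary fibrosis". A non-fatal exacerbation not attributed to nintedanib is outside that scope.

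**How large a loss would matter**

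Inputs: n = 300 (Protocol 9.6); one-year exacerbation incidence 14.2% and annual acute worsening of 5–10% (Protocol 7.4). The fraction of events lost, f, is not in the documents.

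- Expected patients with an exacerbation in year 1: 300 × 0.142 = 42.6.
- 95% half-width: 1.96 × √(0.142 × 0.858 / 300) = 3.95 points.
- Reported incidence is 14.2 × (1 − f): 14.2% at f = 0, 12.8% at f = 0.10, 10.2% at f = 0.28.
- Bias equals the half-width at f = 3.95 / 14.2 = 27.8%, or 0.278 × 42.6 = 11.8 patients.
- At 10% per year: half-width 3.39 points, break-even 33.9%. At 5%: 2.47 points, 49.3%.

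**How much follow-up lies in an interval that ends in death**

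Assume exponential survival from enrolment with hazard h = ln 2 / median. Protocol 7.4 gives a median of 2–3 years from diagnosis and says this may be too low, so 5 years is added as an assumption. For a visit interval from a to a + w, the expected time per enrolled patient between the visit at a and a death inside the interval is

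e^(−ha) × [(1 − e^(−hw)) / h − w·e^(−hw)].

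Sum this over 0–3, 3–6 and 6–12 months, and divide by total first-year time, (1 − e^(−12h)) / h, with h per month:

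| Median survival | Time in intervals ending in death (months) | Total time (months) | Share | 14.2% would read |
|---|---|---|---|---|
| 2 years | 0.123 + 0.113 + 0.390 = 0.625 | 10.141 | 6.16% | 13.3% |
| 3 years | 0.083 + 0.079 + 0.286 = 0.448 | 10.715 | 4.18% | 13.6% |
| 5 years (assumed) | 0.051 + 0.049 + 0.185 = 0.285 | 11.205 | 2.54% | 13.8% |

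(Terms are rounded; sums use unrounded values.) The last column is 14.2 × (1 − share). It assumes that exacerbations are unrelated to death and that none in these intervals is recorded elsewhere.

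Over 24 months with 300 patients, the same model puts 30.7 of 432.8 person-years (7.1%) in such intervals at a 2-year median and 23.2 of 480.5 (4.8%) at 3 years. At 5–10% per year, that is about 1.2 to 3.1 worsening events out of 21.6 to 48.0.

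**The case against.** The strongest reply is that SAP 6.7 concerns baseline values and by-visit tables, so the sentence may only mean that off-schedule measurements stay out of those tables. It does not expressly discard dated events. The section's own exception counts against this reading: if event data were already outside the exclusion, there would be no need to bring adverse events back in.

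Second, many records do not depend on visit type. Deaths, hospitalisations, comorbidities and drugs carry dates, withdrawn patients should have a final evaluation, and acute exacerbation is a coded cause of death, so a fatal one is recorded in any case. This stands, and it narrows the exposed group to mainly non-fatal events shortly before death, transplantation or loss of contact.

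Third, the eCRF and display plan are not available. If event pages are dated logs analysed by date, or unscheduled visits have no form, the rule may remove nothing. This also stands, and it is why the size cannot be stated.

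Fourth, the modelled shift is small: 0.36 to 0.88 points against a half-width of 3.95. It also applies survival from diagnosis as if it ran from enrolment, and n = 300 is not the newly diagnosed stratum that Protocol 9.8.1 treats as decisive. With an assumed 100 such patients, the half-width is 6.84 points and the break-even loss 48%. These limits are fair for the illustration but do not remove the contradiction.

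Finally, SAP section 7 plans frequencies and does not mention the incidence rates of Protocol 9.8.1. That is a separate gap, which the fix here would not close.

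**Conclusion.** The concern holds. SAP 6.7 conflicts with Protocol 9.3.3 on whether unscheduled visits are foreseen and, read literally, with Protocol 9.8.1 on which events are described. It reaches outcomes that SAP 5.1 calls primary, and the adverse-event exception is too narrow to restore them.

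The size is unknown and may be nil. Under the illustrative survival model the shift is under one percentage point. It would be larger if non-fatal exacerbations cluster before death, and smaller if survival is better or the events reach another eCRF page. About 28% of exacerbations would have to be lost before the bias matched the sampling half-width at n = 300. The point should be fixed because the stated rule can only bias event frequencies downward and the correction is cheap. Confidence is medium, because the eCRF structure is not known.

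**What to change.** Amend SAP 6.7 as follows:

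- Limit the exclusion of unscheduled visits to by-visit summaries of continuous measurements.
- State that deaths, clinical events, hospitalisations, comorbidities and dated drug records count by onset date from enrolment to censoring, whatever visit recorded them.
- Check for duplicates on patient, event type and onset date, so that an event entered at both an unscheduled and a nominal visit counts once.
- Delete the statement that unscheduled visits are not expected.

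The cost is two SAP sentences and one programming check. Before finalising, confirm how the eCRF holds events. Table 1 lists only nominal visits, so if unscheduled visits have no form, the event must be entered in a dated event record or on the next planned visit's form for the new rule to have any effect.
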